8.4.5.1 Unrelated Procedures

Diagnostic and therapeutic noninvasive and invasive procedures, such as surgery, should not be reported as AEs. However, a medical condition for which an unscheduled procedure was performed should be reported if it meets the definition of an AE (eg, an acute appendicitis should be reported as the AE and not the appendectomy).

8.4.6 Follow-up of Adverse Events and Serious Adverse Events

All AEs must be followed until they are resolved or until the last safety follow-up visit or the start of new anticancer treatment, whichever comes first.

All SAEs and events qualifying for immediate reporting (see Section 8.4.3) that are ongoing at the safety follow-up visit(s) should continue to be followed on a regular basis until the event has been resolved or until the investigator assesses it as chronic and all queries have been resolved.

8.4.7 Warnings and Precautions

Refer to the IB for detailed information for precautions and warnings for GEN1053.

Additional relevant safety information collected between IB updates will be communicated in the form of investigator notifications. Significant information will be included in the ICF and should be discussed with the subject during the trial as needed.

8.5 Pharmacokinetics

Venous blood samples will be collected for analyzing matrix concentrations of GEN1053 as specified in the Schedule of Activities (Section 1.3). Date and 24-hour clock time of each sample will also be recorded.

Samples collected for GEN1053 PK will be divided into aliquots prior to analysis and may additionally be used to evaluate safety or efficacy aspects to address any concerns that may arise during or after the trial period. Genetic analysis will not be performed on these samples. Subject confidentiality will be maintained.

Samples will be analyzed to determine concentrations of GEN1053 using a validated, specific, and sensitive method by or under the supervision of the sponsor.

Additional information about the collection, handling, and shipment of samples is included in the laboratory manual.

8.6 Pharmacodynamics

Refer to Section 8.7 for pharmacodynamic biomarkers.

8.7 Biomarkers

8.7.1 Biomarker Sample Collection

Samples for biomarker analyses will be collected as specified in the Schedule of Activities. Biomarker analyses are dependent upon the availability of appropriate biomarker assays and clinical response rates. Biomarker analysis may be deferred or not performed, if during or at the end of the trial, it becomes clear that the analysis will not have sufficient scientific value for biomarker evaluation, or if there are not enough samples or responders to allow for adequate biomarker evaluation. In the event the trial is terminated early or shows poor clinical efficacy, completion of biomarker assessments is based on justification and intended utility of the data.

Details on the collection, processing, storage, and shipment of biomarker samples will be provided in separate documents (eg, sample handling sheets, laboratory manual).

All biopsies performed in this trial will be done by trained medical staff including specialized radiologists or surgeons depending on the location of the lesion and according to the local standard of care. Lesions will be selected by the investigator or the radiologist with the best interest of the subject in mind. Biopsies will only be done if there is a low risk of complications for the subject.

8.7.2 Biomarker Assessments in Tumor Samples

A fresh biopsy collected before treatment with trial treatment (ie, during the screening period) is required for all subjects for enrollment. This fresh biopsy must not be older than 6 months and taken after failure/stop of last prior treatment, but before treatment with trial treatment. Documentation of fresh biopsy collection and shipment must be submitted to the sponsor as a part of the eligibility package prior to administration of the first dose of trial treatment. The fresh biopsy should be a core biopsy or resected tissue. A fine needle aspirate will not be sufficient. The following specimen types are not acceptable biopsy samples: cytological specimens, aspirates, bone, or bone marrow. All tumor biopsies should be FFPE. A subject must also provide an archival tumor sample, if available. Refer to Section 8.2.1 for additional information on biopsy procedures related to defining target lesions.

During the trial, an on-treatment biopsy is also required, between Cycle 2 Day 8 and Cycle 2 Day 21 (inclusive) of trial treatment; and if any additional tumor biopsies are collected that are part of normal clinical practice, these will also be examined as described below.

Biomarker analyses in tumor samples at baseline and during treatment may help to confirm the GEN1053 or GEN1053+IM MoAs and enable the identification of biomarkers predictive of response to GEN1053 or GEN1053+IM. Tumor biopsies will be evaluated for target expression (protein or RNA), as well as molecular profiling to identify potential mechanisms of tumor response and/or treatment-induced changes in the immune microenvironment.

8.7.2.1 Protein Expression Analyses

Expression of proteins related to malignant solid tumor biology or GEN1053 and GEN1053+IM MoAs may be evaluated in tumor biopsies by IHC on an automated staining platform. Tumor sections will be scored by a certified pathologist, and digital images will be made from stained tumor sections in order to be used for exploratory digital pathology analyses.

8.7.2.2 RNA Expression Analyses

RNA sequencing may be performed on tumor biopsies to determine CD27, CCI RNA expression levels, as well as to evaluate other potential genes associated with CD27, CCI biology, with immune effector cell activation, or with cancer biology in general.

8.7.2.3 DNA Analyses

Tumor biopsies may also be analyzed using NGS for analyses of DNA mutations, copy number variations, microsatellite instability, indels, and/or rearrangements or polymorphisms in genes associated with CD27, CCI expression or function, GEN1053 and GEN1053+IM proposed MoAs, or cancer biology in general.

8.7.3 Biomarker Assessments in Blood Samples

Biomarker assessments may also be performed using whole blood samples to investigate potential pharmacodynamic markers and explore the relationship to the efficacy and/or MoA of GEN1053 and GEN1053+IM. Assessments will be performed at baseline (before infusion at Cycle 1 Day 1) and during treatment in order to enable correlation analyses with response to treatment or disease biology.

8.7.3.1 *Immunophenotyping Analyses*

Immunophenotyping (eg, measurement of T cells, B cells, NK cells, monocytes, DCs) may be performed at baseline and during treatment at planned visits to evaluate changes associated with the MoA of GEN1053 and GEN1053+IM, subject response to GEN1053 and GEN1053+IM, and disease biology. Target engagement may be determined at baseline and during treatment at planned visits to evaluate changes associated with the MoA of trial treatment, DL, and subject response to trial treatment.

8.7.3.2 *Cytokine or Soluble Factors Analyses*

Cytokine and complement factors (C3a and Bb) analysis may be performed at baseline and during treatment at planned visits to investigate safety and potential pharmacodynamic markers of GEN1053 and GEN1053+IM. sCD27 analysis may be performed at baseline as an exploratory biomarker.

8.7.3.3 Cell-Free DNA/RNA (cfDNA/RNA) and Tumor-Derived DNA (ctDNA) Analyses

cfDNA/RNA, including ctDNA and/or exoRNA, may be measured, and analyses such as RNA expression levels, DNA mutations, copy number variations, microsatellite instability, indels,

Genmab

and/or rearrangements in genes may be performed to evaluate the association of such biomarkers with GEN1053 and GEN1053+IM MoAs, subject response, or disease biology.

A whole blood sample may also be evaluated to confirm the tumor specificity of any genomic alterations that are identified. Where required by local or country specific regulations, each subject must sign a separate ICF indicating agreement to provide samples for genomic biomarker analysis (DNA/RNA).

If DNA/RNA research evaluations are performed, the results may be reported in a separate report.

8.8 Immunogenicity

Venous blood samples will be drawn for analysis of ADAs in serum samples as per the time points specified in the Schedule of Activities (Section 1.3).

Samples will be screened for ADAs binding to GEN1053 and the titer of confirmed positive samples will be reported. Neutralization characterization of ADAs may also be performed using appropriate methods.

Further details are included in the laboratory manual.

Samples will be collected to evaluate the presence of ADAs against GEN1053 in monotherapy as well as in the combination cohorts. Samples collected for ADAs to GEN1053 in monotherapy as well as in combination therapy, may additionally be used to evaluate safety or efficacy aspects that address any concerns arising during or after the trial period for further characterization of immunogenicity. Genetic analyses will not be performed on these serum samples. Subject confidentiality will be maintained.

9 STATISTICAL CONSIDERATIONS

The statistical analysis of the data collected in this trial is the responsibility of the sponsor. A description of the statistical methods to be used to analyze the data is outlined below. The analyses will be detailed further in the SAP.

The SAP will be developed and finalized before database lock and will describe the subject populations to be included in the analyses, and procedures for accounting for missing, unused, and spurious data. This section is a summary of the planned statistical analyses of the primary and secondary endpoints.

All presentations will be done separately for the Dose Escalation part and the Expansion part. Subjects in the Dose Escalation part will typically be analyzed according to the DL received. Subjects in the Expansion part will be analyzed according to their assigned Expansion cohort. Exploratory analyses may be considered for HNSSC subjects crossing over from GEN1053 to GEN1053+IM due to PD.

The main analyses will be timed as follows:

- Interim analysis, Monotherapy Dose Escalation phase 1a and Combination therapy Dose Escalation phase 1b: Main safety and pharmacodynamic analyses will be conducted on all subject data at the end of the escalation (upon completion of DLT evaluation of the last subject in the Escalation phase).
- **Primary analysis, Expansion phase 2a**: The Expansion part consists of parallel cohorts, wherein each Expansion cohort may report its individual main analysis. Main safety, pharmacodynamic and efficacy analyses will be conducted at the time all subjects who are still receiving trial treatment have at least 2 postbaseline scans performed (such that the exploratory efficacy endpoints can be assessed) or have completed the safety follow-up period or have ended the trial.

9.1 Statistical Hypotheses

Due to the early stage of this trial, no formal hypothesis testing for confirmative purposes will occur.

9.2 Sample Size Determination

No formal sample size calculation was performed.

In the Dose Escalation and Expansion parts:

- In the Monotherapy Dose Escalation phase 1a: up to 63 (maximum 9 subjects at each DL) subjects who are ≥18 years of age and have malignant solid tumors will be treated.
- In the Combination therapy Dose Escalation phase 1b: up to 27 subjects (maximum 9 subjects in each cohort)
- In the Expansion phase 2a: approximately 80 subjects (approximately 40 for each cohort).

For the Expansion part, a sample of 40 per cohort is deemed enough to provide a preliminary assessment of efficacy. A sample size of 40 subjects would ensure at least 90% power to detect a shift to an ORR of 30% from a base rate of 10% given a 1-sided binomial test at a 5% significance level. In addition, efficacy monitoring will be applied as described in Section 9.5.

9.3 **Populations for Analyses**

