Statistics	For the Dose Escalation part, no formal sample size calculation was performed. The Dose Escalation part will enroll subjects from a range of cancer types. In phase 1a, a Bayesian logistic regression model (BLRM) will be used to guide the choice of GEN1053 monotherapy dose. In phase 1b, the choice of an optimal combination dose will be guided by Bayesian optimal interval method (BOIN), with a flat DL of IM, but could potentially consider different DLs of IM. For the Expansion part, no formal sample size calculation has

	been conducted, but 40 subjects would ensure at least 90% power to detect a shift to an ORR of 30% from a base rate of 10% given a 1-sided binomial test at a 5% significance level. A futility analysis will be conducted after 10 and/or 20 subjects to estimate the predictive probability of success. The probability of success estimate will be updated as data accumulates.
GCP	This trial will be conducted in compliance with the principles of the Declaration of
Compliance	Helsinki, the International Council for Harmonisation Good Clinical Practice ICH GCP
	E6(R2), and applicable regulatory requirements.

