9.5 Efficacy Monitoring in Expansion Cohorts

The Expansion part will be conducted in at least 2 tumor types using the Bayesian PPoS with a maximum sample size of 40 per indication and treatment (both mono- and combination therapy).

The efficacy in each Expansion cohort will be monitored utilizing the Bayesian efficacy monitoring via predictive probabilities (Lee and Liu, 2008). In particular, the PPoS will be calculated when (at minimum) 2 scans from the first 10 subjects in the Expansion cohort have been locally reviewed. The next futility inspection takes place when data from 20 subjects have been locally reviewed.

At the end of the Expansion cohort, the success criteria are defined as the posterior probability that the confirmed ORR exceeds the ineffective ORR threshold (p_0) with at least 80%. The weights correspond to how likely each outcome is.

If the predicted probability of success is less than 10% the monotherapy Expansion cohort is judged as likely being "futile." However, the threshold of 10% is not considered as a binding futility bar as the Expansion cohort at this stage still is under explorative investigation. The enrollment into the Expansion cohort may also continue (up to maximum 40 subjects) while the scans necessary to derive the response rates in the initial 20 subjects are obtained and reviewed. For the combination therapy Expansion cohort, a 30% threshold determines whether further investigation is judged "futile" or "non-futile." However, again, the criterion is nonbinding.

The ineffective ORR thresholds are tabulated in Table 9-2, with the rates considered to warrant further evaluation of GEN1053 as mono- or combination therapy (p_1) . Based on p_0 , the number of responders required at the monitoring time to consider the data as a likely "success" (by each case) is presented in Table 9-3.

For calculations, the Bayesian Efficacy Monitoring via Predictive Probability application v1.1.4 at www.trialdesign.org has been utilized, based on the following design parameters:

- Beta(p₀,1-p₀) as prior distribution for the response rate
- No early stopping for efficacy

Table 9-2The Ineffective ORR Threshold and the Response Rates That Warrant
Further Evaluation of the Drug

Cancer Type	Case A: Mono Therapy HNSCC	Case B: Combination Therapy NSCLC	
$\begin{array}{l} \text{Ineffective ORR threshold} \\ (\text{ORR} \leq p_0) \end{array}$	p ₀ =10%	p ₀ =15%	
ORR that warrants further evaluation of the drug	p1=25%	p1=30%	

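### The 90% power statement for 40 subjects uses response rates and a test that belong to neither Expansion cohort; the plan's own table gives 91% success with 17% false success (HNSCC) and 76% with 10% (NSCLC)

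*Combined protocol and SAP*

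**What the plan says.** Section 9.2 opens with "No formal sample size calculation was performed". It then judges 40 per cohort sufficient for a preliminary look at efficacy and adds: "A sample size of 40 subjects would ensure at least 90% power to detect a shift to an ORR of 30" per cent, against a base rate of 10%, with a 1-sided binomial test at 5%. The Statistics row of the synopsis (Section 1.1) makes the same claim: "40 subjects would ensure at least 90% power to detect a shift to an ORR of 30% from a base rate of 10" per cent. Neither place names a cohort or calls the figures illustrative.

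Section 9.5 sets out how the cohorts will be judged:

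- **Rates (Table 9-2).** The ineffective rate p0 is 10% for HNSCC monotherapy (Case A) and 15% for NSCLC combination (Case B). The row labelled "ORR that warrants further evaluation of the drug" gives p1 = 25% and 30%.
- **Final rule.** "At the end of the Expansion cohort, the success criteria are defined as the posterior probability that the confirmed ORR exceeds the ineffective ORR threshold". This probability must reach 80% or more. Table 9-3 translates this to ≥6/40 (A) and ≥9/40 (B).
- **Futility.** The predictive probability of success (PPoS) is compared with 10% (monotherapy) or 30% (combination). On timing, for each cohort: "PPoS will be calculated when (at minimum) 2 scans from the first 10 subjects in the Expansion cohort have been locally reviewed", and again at 20 subjects. The looks do not bind: "However, the threshold of 10% is not considered as a binding futility bar", and the same is said of the 30% bar. The synopsis words the timing differently: "A futility analysis will be conducted after 10 and/or 20 subjects".
- **Operating characteristics (Table 9-3).** Success is 17% at p0 and 91% at p1 for Case A, and 10% and 76% for Case B. The 10-subject entry for Case A reads N/A.

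**The concern.** The 10%/30% pair takes a null that matches HNSCC and an alternative that matches NSCLC. That is a 20-point difference, where each cohort is set up around 15 points (25 − 10 and 30 − 15). The 5% binomial test is also not the rule that decides either cohort.

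So the only power and error rate stated in Section 9.2 and the synopsis apply to neither cohort. Someone reading only the synopsis would take away at least 90% power at 5% error for both. For NSCLC the gap is mainly in power, and for HNSCC mainly in error. Because the plan disclaims a formal calculation and confirmatory testing, no decision rule is affected. What is at stake is whether the stated justification for 40 subjects is accurate.

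**Working it through.** **Inputs.** n = 40 and the 10%/30%, 1-sided 5% statement (Section 9.2); p0/p1 of 10%/25% and 15%/30% (Table 9-2); priors Beta(p0, 1−p0), 80% posterior cut, and 10% and 30% PPoS thresholds (Section 9.5).

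**1. Reproduce the stated power.** With X ~ Binomial(40, p), take the smallest c with P(X ≥ c | p0) ≤ 0.05, then find P(X ≥ c | p1).

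- At p0 = 0.10: P(X ≥ 7) = 0.0995 and P(X ≥ 8) = 0.0419, so c = 8.
- Power at 0.30: P(X ≥ 8) = 0.9447.

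The statement of at least 90% is correct for its own inputs.

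**2. Same test at each cohort's own rates.**

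- HNSCC, 10% against 25%: c = 8, alpha 0.0419, power 0.8180.
- NSCLC, 15% against 30%: P(X ≥ 10) = 0.0672 and P(X ≥ 11) = 0.0299, so c = 11 and power is 0.6913. The next cut, ≥10, exceeds 5% and still gives only 0.8041.
- The ≥8/40 cut implied by the sentence, at the 15% rate called ineffective for NSCLC: P(X ≥ 8) = 0.2441.

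**3. Planned final rule.** The posterior after x responses in 40 is Beta(p0 + x, 1 − p0 + 40 − x).

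- Case A: P(ORR > 0.10) is 0.648 at x = 5 and 0.807 at x = 6, so ≥6/40.
- Case B: P(ORR > 0.15) is 0.775 at x = 8 and 0.877 at x = 9, so ≥9/40.

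Both match Table 9-3.

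**4. Futility cuts.** With x responses in n subjects and final cut r, PPoS is the beta-binomial probability of at least r − x responses among the remaining 40 − n, with parameters p0 + x and 1 − p0 + n − x.

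- Case A, 10% threshold: 0.007 at 0/10 and 0.247 at 1/10; 0.028 at 1/20 and 0.185 at 2/20. Continue at ≥1/10 and ≥2/20.
- Case B, 30% threshold: 0.098 at 1/10 and 0.381 at 2/10; 0.132 at 3/20 and 0.370 at 4/20. Continue at ≥2/10 and ≥4/20.

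**5. Exact operating characteristics of the planned rule.**

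| Cohort and looks | Futile at p0 / p1 | Success at p0 / p1 | Table 9-3 prints |
|---|---|---|---|
| HNSCC, ≥1/10 and ≥2/20 | 0.4838 / 0.0669 | 0.1749 / 0.9056 | 48%/7%; 17%/91% |
| HNSCC, ≥2/20 only | 0.3917 / 0.0243 | 0.1932 / 0.9431 | – |
| HNSCC, looks not acted on | – | 0.2063 / 0.9567 | – |
| NSCLC, ≥2/10 and ≥4/20 | 0.7200 / 0.1917 | 0.0963 / 0.7625 | 72%/19%; 10%/76% |
| NSCLC, looks not acted on | – | 0.1354 / 0.8890 | – |

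The printed Case A row matches when a ≥1/10 look is included and does not match without it. The plan's own 10% threshold produces that look (0.7% at 0/10, 24.7% at 1/10), and Section 9.5 schedules it for each cohort, so the N/A does not agree with the figures beside it.

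**The case against.** The strongest reply is that the sentence is true and claims little. Section 9.2 disclaims a formal calculation, Section 9.1 rules out confirmatory testing, and ORR is a secondary endpoint. The 10% base rate is HNSCC's own p0, so for that cohort the sentence gives a correct power at a true ORR of 30%. At HNSCC's own 25% the planned rule does reach 91%. Section 9.2 also points straight to Section 9.5, where the cohort figures are printed openly. The NSCLC 76% assumes both non-binding looks are followed; if they are not, it is 89%, about one point short of 90%. The 69% partly reflects the discreteness of the exact test, since its actual alpha is 3.0%. The ≥8/40 cut is never used for NSCLC. The Case A N/A is a separate matter from the power sentence.

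Much of this stands, and it limits the seriousness: no decision depends on the sentence, and the shortfall for NSCLC under the planned rule is a range of 76% to 89%, not a single figure. It does not remove the conflict. The sentence directly supports the 40 per cohort, is not marked as an example, and appears in the synopsis without any Table 9-3 figures. Section 9.2 presents the Section 9.5 monitoring as an addition to that power, not a replacement for it. The documents do not show how the 10%/30% pair was chosen; the point is only that it matches neither column of Table 9-2.

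**Conclusion.** The concern holds; it should be fixed, though it does not undermine the design. On exact calculation, neither cohort has 90% power at 5% error:

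- **HNSCC** has 82% power on the stated test. Under the planned rule it has 91% to 96% success at 25%, with 17% to 21% false success at 10%.
- **NSCLC** has 69% on the stated test. Under the planned rule it has 76% to 89% success at 30%, with 10% to 14% false success at 15%.

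The first figure in each range assumes both futility looks are followed and the second that neither is acted on. All figures assume exactly 40 evaluable subjects per cohort and the priors, thresholds and rates in Section 9.5. Separately, the N/A for Case A is inconsistent with the figures printed in its own row.

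**What to change.** In Section 9.2 and the synopsis, replace the power sentence with wording such as:

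> With 40 subjects per cohort and the Section 9.5 rule, if the futility looks are followed, the chance of meeting the success criterion is 91% at a true ORR of 25% and 17% at 10% (HNSCC), and 76% at 30% and 10% at 15% (NSCLC). If the non-binding looks are not acted on, these are about 96% and 21% (HNSCC), and 89% and 14% (NSCLC).

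If the 5% binomial test is kept as a reference, label it as such and give 82% (HNSCC) and 69% (NSCLC).

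In Table 9-3, reconcile the Case A N/A with the ≥1/10 look its figures imply, and align the synopsis wording on looks at 10 and/or 20 subjects with Section 9.5. If no 10-subject look is intended for HNSCC, the Case A figures become about 94% success at 25% and 19% at 10%, with futility of 2% and 39%.

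The cost is the replacement sentence in two places, the synopsis wording on the looks and one table row, with less favourable stated figures. Sample size, decision rule and conduct do not change. The edits can go into the substantial amendment that Section 4.2.2 already requires before phase 1b and Expansion cohort 2. That section does not tie the opening of the HNSCC cohort to the amendment, so the HNSCC text should be corrected earlier if that cohort is to open first.
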